3.4.3 Treatment with corticosteroids

The optimal dose of steroid and duration of therapy for GVHD is unknown and there is considerable variation in practice, particularly in early stage GVHD, but in general steroid dose should be sufficient to treat GVHD but limited to avoid any side effects of long-term high dose therapy. The preferred rate to taper steroids is also not well-established⁹¹, but general guidelines have been provided in the design of a recent randomized, prospective, multi-center trial (BMT CTN 0802) comparing steroids/placebo vs. steroids/MMF for acute GVHD^{6,17}. It is suggested that patients receive an initial steroid dose by IV route (usually methylprednisolone) that is equivalent to prednisone at a dose 2 mg/kg/day at diagnosis of acute GVHD. Steroids can be tapered as tolerated according to individual practice. It is suggested that steroids are tapered if signs of clinical improvement defined as any clinically recognizable lessening of skin rash, redness, or extent; lessening of diarrhea or lowered bilirubin (though it does not have to be greater than or equal to one stage improvement in any involved organ), without worsening in any organ.

Suggested steroid taper for responders (round to nearest 5mg of prednisone)	
Day 1-5	Prednisone 2 mg/kg/day (use IV methylprednisolone equivalent in single or divided dose(s))
Day 6-10	Prednisone 1.5 mg/kg/day PO (or IV methylprednisolone equivalent)
Day 11-15	Prednisone 1 mg/kg/day PO (or IV methylprednisolone equivalent)
Day 16-20	Prednisone 0.5 mg/kg/day PO (or IV methylprednisolone equivalent)
Day 21-28	Prednisone 0.25 mg/kg/day (or equivalent) PO (or IV methylprednisolone equivalent)
Day >28	Continue taper with a goal of <0.2 mg/kg/day of prednisone PO once daily (or equivalent).

Table 3 – Suggested steroid taper**3.4.4 Additional immunosuppressive therapy****3.4.4.1 Standard GVHD prophylaxis**

Most patients will receive medications that are considered GVHD prophylaxis as part of their transplant regimen. Patients developing acute GVHD during GVHD prophylaxis therapy (e.g. calcineurin inhibitor, sirolimus, MMF, etc.) should have this medication continued during the study if possible. Patients who have been tapered off of or completed standard calcineurin inhibitor based prophylaxis (e.g. cyclosporine, tacrolimus) can be restarted on this medication concurrent to treatment on this

Abbreviated Title: Early BMSC Pilot for Acute GVHD

Version Date: 6/16/2016

protocol. Concurrent or addition of topical steroid therapy (skin creams, oral budesonide, or other locally acting steroid preparation) is allowed.

3.4.4.2 Progression of GVHD

If there is no response to therapy or acute GVHD progresses, then the patient can be treated by adding one of many alternative systemic secondary GVHD therapies. BMSC therapy will continue per protocol design, given the prior established efficacy of BMSC in refractory GVHD and the poor outcomes associated with primary refractory and progressive acute GVHD.

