2.4.2 De novo GVHD

Kebriaei *et al.* conducted the first prospective trial of third-party BMSC for the treatment of *de novo* acute GVHD using a pre-manufactured, universal donor formulation of BMSC (Prochymal®)⁵⁴. This industry sponsored, randomized, multicenter trial compared two different dose levels of BMSC (2 or 8x10⁶ BMSC/kg) combined with standard corticosteroid therapy. Patients were infused with BMSC within 72 hours of acute GVHD diagnosis and they received one additional dose 3 days later. Of 31 adult patients, 71% had a CR at day 28 after therapy (primary endpoint), and the initial ORR was 94%. No evidence of a dose response relationship was seen. These promising results led to the use of Prochymal® in a large industry-sponsored phase III trial for *de novo* acute GVHD (Protocol 265, Osiris Therapeutics, Inc.). The primary endpoint was CR within 28 days of treatment administration, and treatment failures included patients without CR at 28 days and those requiring increased doses of corticosteroids or additional immunosuppressive therapy. This study failed to reach significance in the primary endpoint, and the results have not been published⁵⁵. The higher than historically reported response to steroid therapy, the use of late passage BMSC, the predominance of skin GVHD, and the choice of primary endpoint at day 28 are widely attributed to have been the cause for failure to meet the primary endpoint^{56,57}.

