3.4.4.3 Flare of GVHD

If acute GVHD flares during taper of steroids or GVHD prophylaxis medications, steroid or GVHD prophylaxis dosing may be re-escalated or secondary therapy added at the discretion of the treating physician. Re-escalation of steroid or GVHD prophylaxis medications for GVHD flare alone will not be considered as need for secondary therapy.

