3.4.6 Concurrent Treatments

Subjects may receive any concurrent treatment except other investigational agents for treatment of acute GVHD (See [PBSCT Supportive Care Guidelines](#))

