11.2 Secondary Endpoints

Secondary endpoints for this study are:

- Proportions of complete response (CR), partial response (PR), mixed response (MR), no response (NR), and worsening disease (WD) among surviving patients at day +28 and +56 of study (Appendix 2). Need for secondary immunosuppression by day +28 and +56 of study. Steroid dose (prednisone equivalent) at day +28 and +56 of study. Proportion of responses in patients with high and low ST2 levels.

Secondary endpoints will not be used in assessing success or failure of the primary endpoint but are undertaken for descriptive or exploratory research and will be reported accordingly. The duration of treatment limiting toxicity monitoring will be 3 weeks after the last dose of BMSC. The total duration of treatment limiting toxicity monitoring will be 7-11 weeks. Total serious adverse event monitoring will continue until at least 3 weeks after the last dose of BMSC, and subjects experiencing adverse events related to BMSC will be monitored until toxicity resolution or stabilization.

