Appendix 2: Criteria for Response to BMSC

Term	Definition
Complete response (CR)	Resolution of acute GVHD in all involved organs
Partial response (PR)	Organ improvement of at least 1 stage without worsening in any other organ system
Overall response (OR)	CR or PR
Mixed response (MR)	Improvement by at least 1 organ stage in at least 1 evaluable organ with worsening by at least 1 organ stage in at least 1 other organ
Stable disease	The absence of any clinically significant differences (improvement or worsening) sufficient to meet minimal criteria for improvement or deterioration in any evaluable organ
Worsening disease	Deterioration in at least 1 evaluable organ by 1 stage or more
No response	MR or stable disease or worsening disease

Abbreviated Title: Early BMSC Pilot for Acute GVHD**Version Date: 6/16/2016****Appendix 3: Study Calendar for Early BMSC Pilot for Acute GVHD**

Procedure	Protocol Screen												Before and after each infusion +/- 24 hours ^{b, g}	3 weeks after last infusion +/- 7 days	Post Therapy Follow-up ^c
		Day 0 +/- 24 hrs	Week 1	Week 2	Week 3	Day 28 +/- 72 hrs	Week 5	Week 6	Week 7	Day 56 +/- 72 hrs					
History	X														
Physical Exam	X														
Vital signs: BP, HR, RR, Temp, pulse ox	X														
Acute GVHD evaluation	X ^a	X	X	X	X	X	X	X	X	X			X		
Performance Score (KPS)	X														
Labs															
• Pregnancy Test ^c	X														
• CBC/differential	X												X	X	
• Chemistry Panel	X												X	X	
BMSC INFUSION^f													X		
Correlative Research Studies ^g		X										X	X		
Response evaluation ^d						X				X			X		
Adverse events		X	X	X	X	X	X	X	X	X			X	X	
Concomitant Medications		X				X				X			X	X	

^a Tissue biopsy if indicated: See Appendix 1 for GVHD staging. aGVHD evaluation may occur in inpatient or outpatient setting and will occur at minimum on days of BMSC infusion (+/- 24 hours) and at any additional time that is determined necessary by the investigators. aGVHD evaluation will be done at least once weekly for the duration for the first 56 days of treatment.

^b Monitoring according to NIH Clinical Center SOP: [Administration of Products of Cellular Therapy](#)

^c In females of child-bearing potential

^d Response assessment according to condition; response criteria in Appendix 2.

^e Follow up between infusions and after the last BMSC infusion will be based on the subject's condition, as frequently as twice weekly.

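### Day +28 and +56 response is scored regardless of second-line GVHD therapy and is not cross-tabulated with it, so the reader cannot tell how many responses followed rescue

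*Combined protocol and SAP*

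**What the plan says.** **Rescue is allowed and does not end study treatment.** On non-response or progression, section 3.4.4.2 states "then the patient can be treated by adding one of many alternative systemic secondary GVHD therapies" and "BMSC therapy will continue per protocol design". For a flare, section 3.4.4.3 states "steroid or GVHD prophylaxis dosing may be re-escalated or secondary therapy added at the discretion of the treating physician". Section 3.4.6 is equally open: "Subjects may receive any concurrent treatment except other investigational agents for treatment of acute GVHD".

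**Response looks only at organs.** Appendix 2 defines CR as "Resolution of acute GVHD in all involved organs". PR is an improvement of at least one organ stage with no other organ worse. Neither definition has a condition on added therapy.

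**The two outcomes are listed side by side but not linked.** Section 11.2 gives the response categories among surviving patients at day +28 and +56, and separately "Need for secondary immunosuppression by day +28 and +56 of study". It also lists steroid dose at both days and response in high and low ST2 patients. No section scores a rescued subject as a non-responder, excludes that subject, or plans a cross-table of response by rescue.

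**Part of the boundary is drawn.** Section 3.4.4.3 adds: "Re-escalation of steroid or GVHD prophylaxis medications for GVHD flare alone will not be considered as need for secondary therapy". This says what does not count as secondary therapy. No section says what does.

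**The concern.** The secondary objective (section 1.1.2) is to estimate the efficacy of the study regimen, which the protocol summary describes as BMSC added to upfront corticosteroids. Second-line agents are not part of that regimen. Yet a subject whose GVHD progresses, who receives a second-line agent and whose organs clear by day +28 or +56 is recorded as a CR, under an appendix titled as response to BMSC.

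Two readings are affected:

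- **Overall response.** It is the trial's main clinical efficacy output, and the share of it that followed rescue would not be visible.
- **Response by ST2.** The summary presents ST2 as a predictor of steroid resistance and asks whether BMSC can prevent progression in biomarker-high-risk patients. If rescue is more frequent in the high-ST2 group, which is plausible but not stated, counting responses after rescue could narrow the contrast that the study wants to describe.

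**Working it through.** **Step 1. The plan's own figure.** The only stated power is for the primary endpoint (section 11.3.2): N = 23, null 75%, alternative 95%, one-sided 0.05, exact binomial. With rejection at 21 or more of 23 (section 11.3.4.2):

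- P(X ≥ 21 | n = 23, p = 0.75) = 0.0492
- P(X ≥ 21 | n = 23, p = 0.95) = 0.8948, which matches the stated 89.5%

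A cut-off of 20 gives a type I error of 0.137, and a cut-off of 22 gives a power of 0.679, so 21 is the correct cut-off. None of this involves response, so rescue does not touch it. No sample size or power is stated for the response endpoints.

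**Step 2. Direction.** Let n be the subjects assessed, r the share of them rescued before the assessment, and q the share of the rescued scored CR or PR. On one denominator:

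planned proportion − rescue-as-failure proportion = r × q ≥ 0

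The planned figure therefore cannot be the lower of the two.

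**Step 3. What the separate proportions reveal.** As an assumed example, take 23 assessed, 16 responders and 7 rescued.

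- Largest overlap: min(16, 7) = 7, leaving 16 − 7 = 9 rescue-free responders (9/23 = 39.1%)
- Smallest overlap: max(0, 16 + 7 − 23) = 0, leaving 16 (16/23 = 69.6%)

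The same two published proportions fit a rescue-free response anywhere from 39% to 70%.

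**Step 4. Size.** The documents give neither r nor q, so both are assumed. Difference in percentage points, r × q:

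| Rescued (r) | q = 30% | q = 50% | q = 70% |
|---|---|---|---|
| 10% | 3 | 5 | 7 |
| 20% | 6 | 10 | 14 |
| 30% | 9 | 15 | 21 |
| 40% | 12 | 20 | 28 |
| 50% | 15 | 25 | 35 |

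With 23 assessed, 3 to 35 points is 0.03 × 23 = 0.7 to 0.35 × 23 = 8.1 subjects.

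**Step 5. One case inside that range.** Assume all 23 are alive at the assessment, 12 respond without rescue, and 4 more respond after rescue.

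- Rescue as failure: 12/23 = 52.2% (exact 95% CI 30.6 to 73.2)
- Planned scoring: 16/23 = 69.6% (exact 95% CI 47.1 to 86.8)
- Difference: 4/23 = 17.4 points, due to the scoring rule alone

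**The case against.** **The planned scoring is a coherent choice.** Section 3.4.4.2 continues BMSC after rescue on purpose and gives a reason. Organ status at a fixed day, whatever was added, describes that strategy as delivered; treating rescue as failure answers a different question. This stands. A reader might infer that the planned response rate is simply overstated, but that follows only if rescue-free response is the intended quantity, and the plan does not say so. The planned analysis should therefore stay.

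**The endpoints are descriptive and rescue is already reported.** Section 11.2 says that secondary endpoints do not decide the primary endpoint, and section 11.3.1 would not prevent a cross-table. This limits the weight of the point. It does not remove it, because the two proportions alone do not give the overlap (step 3) and no cross-table is planned.

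**The size is not known.** A reader might take the 61% to 75% response rates of some refractory series in section 2.4.3 as the response after rescue. Those are responses to BMSC, which subjects here already receive, and other series in the same table are much lower (one reports 1 CR and 1 PR among 13 patients). They do not measure the effect of a rescue drug. Nor would every responder after rescue have failed on steroids and continued BMSC, so r × q measures the difference between scoring rules, not the rescue drug's effect.

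**Comparability with the earlier phase III trial.** Section 2.4.2 reports that in that trial "treatment failures included patients without CR at 28 days and those requiring increased doses of corticosteroids or additional immunosuppressive therapy". A reader might infer that a rescue-as-failure figure could be set beside its result. The documents do not support that: the trial also failed patients for steroid increases, which section 3.4.4.3 does not count when given for flare alone, and its endpoint was CR within 28 days.

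**Conclusion.** The point holds as a gap in how a descriptive secondary endpoint is reported. The planned CR and PR proportions at day +28 and +56, overall and by ST2 group, can include responses reached after second-line systemic therapy, and the planned output does not show how many. The direction is certain on a common denominator. The 3 to 35 points rest entirely on the assumed ranges of 10% to 50% rescued and 30% to 70% of those scored CR or PR, and day +28 and day +56 may differ. The documents do not show that the primary TRSAE test, the sample size, the power or the stopping rule is affected, or that the planned scoring is wrong in itself.

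**What to change.** Keep the planned response analysis. Add to section 11.2:

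- CR and CR+PR at day +28 and day +56, overall and by high and low ST2, with subjects who started new secondary systemic GVHD therapy before that assessment counted as non-responders.
- The same denominator as the planned proportions (surviving patients at that day), so that the gap between the two figures reflects rescue only and does not mix in deaths.
- Exact binomial confidence intervals.

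State for this analysis what counts:

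- **Count:** therapy added under section 3.4.4.2 or 3.4.4.3.
- **Do not count:** re-escalation of steroids or prophylaxis for flare alone (3.4.4.3), MMF already in use at entry (5.1.2), or prophylaxis continued or restarted (3.4.4.1).

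This is an analysis rule only and leaves treatment of subjects unchanged. Need for secondary immunosuppression by both days is already an endpoint, and the study calendar already records concomitant medications; start dates are needed to order therapy and assessment. The cost is one extra table, and a second response figure that is the same as or lower than the planned one. The rule should be fixed before response results are examined.

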3.4.4.3 Flare of GVHD

If acute GVHD flares during taper of steroids or GVHD prophylaxis medications, steroid or GVHD prophylaxis dosing may be re-escalated or secondary therapy added at the discretion of the treating physician. Re-escalation of steroid or GVHD prophylaxis medications for GVHD flare alone will not be considered as need for secondary therapy.

3.4.5 Retreatment with BMSC

There will be no retreatment with BMSC infusions after BMSC treatments are stopped.

3.4.6 Concurrent Treatments

Subjects may receive any concurrent treatment except other investigational agents for treatment of acute GVHD (See [PBSCT Supportive Care Guidelines](#))

3.5 TOXICITY

BMSC infusion toxicity will be defined as alteration in vital organ function within the 11 weeks of the study that cannot be explained by other complications; for example, post-stem cell transplant, infections, underlying transplant indication, or other therapy. See Section 8 for definition of Treatment Limiting Toxicity.

3.6 RESPONSE

Subjects will be assessed for response for the primary indication according to criteria listed in Appendix 2. The critical time points for response are at day +28 and day +56. Subjects are considered off protocol after 11 weeks of total enrollment. Subjects will receive additional infusions after day +28 based upon whether or not there is a complete response at the day +28 response assessment (Section 3.4.1). After coming off protocol, subjects will be followed for best response for up to 1 year on their parent transplant protocols.

3.7 SURVIVAL

Survival assessment will be done at day +28 and day +56. After coming off protocol, subjects will be followed for survival for up to 1 year on their parent transplant protocols.

4. RECRUITMENT AND REGISTRATION

The study will be listed on clinicaltrials.gov, clinical center research studies, PDQ, Aplastic Anemia Foundation, and the NHLBI patient recruitment websites. If recruitment goals are not met, a recruitment plan will be developed by the Clinical Center Office of Patient Recruitment to extend the protocol to subjects outside NIH.

Abbreviated Title: Early BMSC Pilot for Acute GVHD

Version Date: 6/16/2016

5. ELIGIBILITY ASSESSMENT

5.1 INCLUSION CRITERIA

5.1.1 History of any grade acute GVHD requiring systemic therapy after allogeneic stem cell transplant or DLI.

Subjects must have received an allogeneic stem cell transplant at NIH and be diagnosed with acute GVHD. Acute GVHD is defined using the NIH consensus definition inclusive of classic acute (≤ 100 days after transplant or DLI, presence of acute GVHD features, absence of chronic GVHD features) AND persistent/recurrent/late onset acute (>100 days after transplant or DLI, presence of acute GVHD features, absence of chronic GVHD features). Subjects with stage I and II skin only (overall Grade I) or isolated upper gastrointestinal involvement are eligible if the treating physician deems that systemic corticosteroid treatment is indicated. Biopsy confirmation of GVHD is desirable, but not required for study entry because enrollment should not be delayed awaiting biopsy or pathology results. Patients must be diagnosed with a first episode of acute GVHD requiring systemic corticosteroids and associated with preceding administration of a cellular therapy including stem cells and donor lymphocyte infusion. Patients who were treated for GVHD associated with another cellular therapy product (e.g. prior allogeneic transplant or DLI) will be allowed into the study.

5.1.2 Previous immunosuppressive therapy

The patient must have received no systemic immune suppressive therapy for treatment of new acute GVHD (e.g. pentostatin, etanercept, denileukin difitox, etc.), except for a maximum 120 hours prior corticosteroid therapy. This does not include immune suppressive therapy for GVHD prophylaxis (e.g. calcineurin inhibitor, sirolimus, MMF, etc.). It is expected that most patients will be receiving GVHD prophylaxis as part of their transplant regimen, thus patients developing acute GVHD while on GVHD prophylaxis will still be considered eligible. Concurrent or addition of locally-acting steroid therapy (skin creams, oral budesonide, or any other locally-acting steroid preparation) is allowed.

There is one exception to the above stipulations: Use of the oral medication MMF (in addition to systemic corticosteroids) for the treatment of acute GVHD will be allowed. MMF is commonly given early in the treatment of acute GVHD, but it has not been shown to improve outcomes compared to steroids alone in a randomized, prospective study; therefore, treatment with MMF will not exclude patients from BMSC treatment.

5.1.3 Age

Age ≥ 4 years old will be allowed.

5.1.4 Birth control

Subjects of childbearing or child-fathering potential must be willing to use a medically acceptable form of birth control, which includes abstinence, while they are being treated on this study.

5.1.5 Informed consent

Signed informed consent and/or assent is required. Assent and educational materials will be provided to, and reviewed with, patients under the age of 18. The informed consent process will begin at recognition of patient eligibility.

*Abbreviated Title: Early BMSC Pilot for Acute GVHD**Version Date: 6/16/2016*

5.2 Exclusion Criteria

5.2.1 Breast feeding or pregnant females (due to unknown risk to fetus or newborn).

5.2.2 Known allergy to gentamicin.

6. CLINICAL EVALUATION

6.1 CLINICAL EVALUATION OF THE SUBJECT

6.1.1 Eligibility Evaluation

- a) Karnofsky performance status
- b) Eligibility to participate in trial
- c) Pregnancy test in females of child-bearing potential
- d) Relevant GVHD organ-specific studies, confirmation of diagnosis, and severity assessment (Appendix 1)
- e) Acute GVHD diagnosed by clinical criteria and no more than 120 hours of prior steroid therapy for diagnosis

Note that eligibility screening may be performed on a separate NIH-CC screening protocol

6.1.2 Pre-Treatment Evaluation

Pretreatment evaluation is to be completed within 30 days of the protocol enrollment date.

- a) Physical examination
- b) Vital signs: temperature, pulse oximetry, blood pressure, respiratory rate, height and weight
- c) CBC with differential + reticulocyte
- d) Chemistry panel (Na, K, Cl, CO₂, Cr, glucose, BUN, albumin, Ca, Mg, Phosphorus, Alk Phos, ALT/AST, total and direct bilirubin, LDH, total protein, CK, uric acid)
- e) As per GVHD evaluation in Appendix 1

6.1.3 Toxicity monitoring

a) Administration and monitoring of BMSC will be performed according to NIH Clinical Center standard operating procedure: [Administration of Products of Cellular Therapy](#).

6.1.4 Follow up Evaluations

- a) Physical exam and performance score
- b) Vital Signs
- c) Routine CBC with differential, Chemistry panel (Na, K, Cl, CO₂, Cr, glucose, BUN, albumin, Ca, Mg, Phosphorus, Alk Phos, ALT/AST, total and direct bilirubin, LD, total protein, CK, uric acid), and reticulocyte count.
- d) Acute GVHD severity and response monitored by skin exam, stool volume, and liver function tests on days of BMSC infusion by the investigators while inpatient and during the day of clinic visit as outpatient.

Abbreviated Title: Early BMSC Pilot for Acute GVHD

Version Date: 6/16/2016

Follow up evaluations after the last BMSC infusion will be based on subject's condition, and may be as frequent as twice weekly. All radiographic examinations at baseline and follow up would be considered standard of care for the evaluation and management of these protocol subjects as clinically warranted.

